8.3. Variables

Variable	Role	Data source(s)
Patient demographics (year of birth, gender, height, weight)	baseline characteristics	Initiation visit
Performance status (ECOG, Karnofsky)	baseline characteristics, potential confounder	Initiation visit Follow up visit
Risk groups (MSKCC risk, Heng risk)	baseline characteristics, potential confounder	Initiation visit
Comorbidities	baseline characteristics, potential confounder	Initiation visit
Lab tests (abnormal findings – levels when abnormal)	baseline characteristics, potential confounder	Initiation visit Follow up visit
Blood Pressure measurement (Y/N, date of exam and level, antihypertensive treatment)	baseline characteristics, outcome	Initiation visit Follow up visit
Electrocardiogram (Y/N/date of exam/ abnormal findings)	baseline characteristics,	Initiation visit
Echocardiography (Y/N/date of exam/ abnormal findings, LVEF)	baseline characteristics,	Initiation visit
Tumor history (date of first diagnosis, TNM, Grade at diagnosis /at enrolment, Histology)	baseline characteristics	Initiation visit
Metastasis (date of first detection and	baseline characteristics	Initiation visit

localisation)		
Previous treatments for RCC (Surgery, radiotherapy, other / for primary tumor/ for metastasis)	baseline characteristics, potential confounder	Initiation visit
Sunitinib therapy (starting date and dose, dose change, change of schedule)	exposure	Initiation visit Follow up visit
Axitinib therapy (starting date and dose, dose titration up, dose reduction, change of schedule)	exposure, effect modifier/sub-group identifier	Initiation visit Follow up visit
Additional anti tumor treatment (name and dose)	exposure, potential confounder	Inclusion visit Follow up visit
Comedications (name of products, starting and ending dates)	exposure, potential confounder	Initiation visit Follow up visit
Sunitinib / Axitinib Progression (Y/N and date)	outcome	Initiation visit Follow up visit
Sunitinib / Axitinib Tumor Response	outcome	Initiation visit Follow up visit
Sunitinib / Axitinib Safety : AE description and AE grade (according CTCAE)	outcome	Initiation visit Follow up visit
Sunitinib / Axitinib discontinuation	outcome	Follow up visit
Axitinib QoL (FKSI-19, and MH and RE domains of SF-36)	outcome	Initiation visit Follow up visit End of treatment
Death (Y/N,date, Cause)	outcome	Follow up visit

Table 1 : variables collected during study

Detailed definitions will be included in the Statistical Analysis Plan

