Progression of the malignancy under study (including signs and symptoms of progression) should not be reported as a serious adverse event/SAR* unless the outcome is fatal within the safety reporting period. Hospitalization due to signs and symptoms of disease progression should not be reported as a serious adverse event/SAR*. If the malignancy has a fatal outcome during the study or within the safety reporting period, then the event leading to death must be recorded as an adverse event/SAR* and as a serious adverse/SAR* event with severity Grade 5.

Medical and scientific judgment is exercised in determining whether an event/reaction* is an important medical event. An important medical event may not be immediately life-threatening and/or result in death or hospitalization. However, if it is determined that the event/reaction* may jeopardize the patient or may require intervention to prevent one of the other outcomes listed in the definition above, the important medical event should be reported as serious.

^{*} Spain requirement only

Axitinib, Inlyta[®]
A4061078 NON-INTERVENTIONAL STUDY PROTOCOL
ADONIS Amended V13
28 Sept 2017

Examples of such events are intensive treatment in an emergency room or at home for allergic bronchospasm; blood dyscrasias or convulsions that do not result in hospitalization; or development of drug dependency or drug abuse.

Additionally, any suspected transmission via a Pfizer product of an infectious agent, pathogenic or non-pathogenic, is considered serious. The event/reaction* may be suspected from clinical symptoms or laboratory findings indicating an infection in a patient exposed to a Pfizer product. The terms "suspected transmission" and "transmission" are considered synonymous. These cases are considered unexpected and handled as serious expedited cases by PV personnel. Such cases are also considered for reporting as product defects, if appropriate.

Hospitalization

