ADONIS CRF Subject ID: Other treatments Additional anti-tumor treatment (e.g. bisphosphonates, other) (the previous visit anti-tumor treatment table is dispalyed) Has additional anti-tumor treatment been changed since last visit (including during this visit)? ☐ Yes □ No If yes please update the table: Medication Dosage Starting date Status __/ ___ ■ Ongoing ■ Discontinued (MM/YYYY) (trade name) End date : ___ / _____ (unit) (dose) (MM/YYYY) □ Ongoing □ Discontinued (MM/YYYY) End date : _ _ / _ _ _ _ (trade name) (dose) (unit) (MM/YYYY) (new lines can be added if more than 2 medications are received) ☐ No Radiotherapy :

Yes Comedications (other than tumor therapy): (the previous visit comedication table is displayed) Have comedications been changed since last visit (including during this visit)? ☐ Yes □ No If yes please update the table: Drug name Starting date Status □ Ongoing □ Discontinued (MM/YYYY) End date ___ / __ ___ (MM/YYYY)) □ Ongoing □ Discontinued (MM/YYYY) End date ___ / __ __ (MM/YYYY)) (new lines can be added if more than 3 treatment s are received)

ADONIS CRF Subject ID: Occurrence of adverse events Has the patient experienced adverse events since last visit? ☐ Yes ☐ No If yes please report the adverse events in the following table and asses the grade using the CTCAE V4.03 (this version is reachable via ta click) Adverse event description Starting date Grade (CTCAE V4.03) □ 2 □ 3 □ 4 (DD/MM/YYYY) □ 1 □ 2 □ 3 □ 4 (DD/MM/YYYY) (new lines can be added if more than AR have occured) Please completed an AE form per AE reported in the table (AE form is attached in annex 2) (The eCRF, automatically completes any section when data are already available; the pre-completed sections are still editable /An AE form per AE is completed The safety requirement as described in the protocol are reminded via a click)

ADONIS CRF Subject ID:

Actions done at the end of this visit with Sunitinib					
☐ Continuation: Please completed this said	me form at the next visit				
☐ Temporary Interruption Please update the					
(the table is disp	layed to the investigator)				
☐ Discontinuation	□ Discontinuation				
If discontinuation, reasons of disco	ontinuation (no multiple selections)				
	Date/ (DD/MM/YYYY)				
☐ Intolerability	Date/ (DD/MM/YYYY)				
main reason:					
☐ Death	Date of death// (DD/MM/YYYY)				
Cause:	☐ tumor-related				
	☐ other cause				
Please observe the definitions and AE rep	orting requirements as defined in the protocol				

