ANNEX 2: ADVERSE EVENT REPORT FORM

Subject ID:

Non Interv	entional Stud	ly Adver	se Eve	nt Report F	Form				Г		F 55			_
			AFR #	(insert when kno	energi				$\neg \vdash$	Locals	For Pfizer i #		Reported	
Pfizer			721		, any				7				-	
PROTOCOL#		'		SUBJECT#								_		
Protocol Title:														
☐ Initial Report [Follow Up Re	eport		Col	untry	where (event	occurr	ed:					
Dat Patient Data	te of Birth			ioity: Asian r(specify)		Black []	lispanio			per local		White _	
	Male 🗌 Female	9	Weight		lb [kg		Height	1		in	Cf	m	
If patient Date has died:	of Death Ca	use(s) of	Death	Determin					_	nown De	eath:			
Patient History	Provide rel	levant me	dical hic	otory below In								-oxic	etina med	lical
☐ None ☐ Unknown				ice is necess									-	
liness (spe	Date	Stop Date		ek bax ngoing			Include		ent Detaik wooedure		d dates			
					[
					[
					[
Study Drug (Trade Ros	e and Generic) ute, Indication	, Formula	ition,	Check box If Pfizer Drug	ı	Dose		Units	Fre	Frequency		T	Stop Date	Check box if Ongoing
												Т		
												T		
							\top					T		
												T		
Concomitant Druge None Unknown	more than	two week	ks befor	gs taken with re the event, dditional copie	and ar	ny drug	used							
Drug Name (Trade	and Generic)			Reaso	on for	Use			Route		Start Date	T	Stop Date	Check box if Ongoing
												\perp		
							\perp					\perp		
Relevant Tests				matory test re page io negeo							nple, from	bloc	od tests, d	liagnostic
Test	Result		Uni	ts	Normal Panne			gh	Comments					
											\perp			
											\perp			
											\perp			

Version3 .May2012

Subject ID:

Non Interv	eport I	Form				For Pfizer internal use only							
	t when inc	num)				Loc	cal#	Date Reported to Pfizer					
Plizer		7.2			, may								
PROTOCOL#			SUB	JECT#	: [
	P	DVERSE EVE	NTS (ii	more th	an two	use ac	lditiona	copieso	f this pag	e)			
		Specify di											
Adverse Event Ten	m					Adverse Event Term							
Onset Date:		_			- 1	Onset D				_			
Is the event seriou If yes, identify serio		_	□ No	•				rious? seriousr	ness crite	eria belo	Yes No		
If yes, identify seriousness criteria below: Seriousness Criteria (Check all that apply): Resulted in death Ufe-threatening Hospitalization/Prolongation of hospitalization Persistent/Significant disability/Incapacity Congenital anomaly/Birth defect						Serious Resu Life- Hosp Pers	sness (ulted in threate bitalizat istent/S genital	Criteria (C death	heck all ngation of disability Birth defe	that app hospita	ply): lization		

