6.2.1 Incidence of Adverse Events (AEs)

- Incidence of AEs: Proportion of patients experiencing at least one AE of any grades by Body system (System Organ Class (SOC) MedDRA);
- Incidence of most common AEs of any grade (occurring in more than 10% of patients in either group) by preferred term (PT) (MedDRA);

The following type of AEs will be described whatever the number and proportion of patients concerned: Diarrhea, hypertension, fatigue, asthenia, hand foot syndrome, nausea, stomatitis, neutropenia, lymphopenia and increased lipase

- Incidence of serious AEs;

- Incidence of non-serious AEs;
- Incidence of all AE per grade, especially grade 3 and 4 AE. Note: all grades should be considered for this analysis and not only worst grade.

AEs will be analysed separately for AEs related to SU or AEs related to AXI treatment

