8.2 STATISTICAL ANALYSES

8.2.1 Safety Analyses

Safety analyses will be provided in the safety population.

AEs will be presented overall and by period of treatment (Sunitinib, Axitinib).

They will be displayed in summary tables, by system organ class (SOC) and preferred term (PT).

The tables will present the number of subjects and the rate of occurrence within each period for which the events occurred. The rate of occurrence will be expressed as a percentage of the subjects from the Safety Analysis Set receiving the treatment concerned.

For the number of subjects and the rate of occurrence, the same classification (SOC and / or PT) in the same patient is counted only once.

In a first time, an overview of all AEs will be given overall and by period of treatment (Sunitinib, Axitinib) and will include the description of the number and the percentage of patients with the following criteria:

- At least one AE
- At least one SAE
- At least one non-serious AE
- At least one grade 3 AE
- At least one grade 4 AE
- At least one grade 3/4 AE

Same analysis will be repeated on related AEs only.

Then each of the following categories of AEs will be described by SOC and PT overall and by period of treatment (Sunitinib, Axitinib):

PFIZER CONFIDENTIAL

Page 28 of 41

- All AEs
- Most common AEs (SOC or $PT \ge 10\%$)
- SAEs
- Non-serious AEs
- Grade 3 AEs
- Grade 4 AEs
- Grade 3/4 AEs

Same analysis will be repeated on related AEs only.

Proportion of patients who discontinued the treatment of interest because of AEs will be given with its 2-sided 95% 'exact' Clopper-Pearson confidence interval overall and by period of treatment (Sunitinib, Axitinib).

Treatment duration until discontinuation for AEs will be analyzed using descriptive statistics (mean, standard deviation, median and range) overall and by period of treatment (Sunitinib, Axitinib).

Proportion of patients who died due to any cause will be given with its 2-sided 95% 'exact' Clopper-Pearson confidence interval overall and by period of treatment (Sunitinib, Axitinib). Causes of deaths (tumor-related, other cause) will also be described.

8.2.2 Analyses of Efficacy Endpoints

Efficacy analyses will be provided in the FAS population.

Primary endpoints

PFS under Axitinib in 2nd line post Sunitinib will be described using the Kaplan Meier method in the SU-AXI subgroup:

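### Protocol 10.3 requires Grade 5 for the event leading to a malignancy death, but the annexed CRF grade fields stop at 4 and the SAP 8.2.1 severity rows stop at grade 3/4

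*Protocol*

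**What the plan says.** Protocol 10.3 (serious adverse events) sets a conditional rule. Where the cancer itself proves fatal while the patient is on study or still in the safety reporting window, the site has to enter what caused the death "as a serious adverse/SAR* event with severity Grade 5". It states no grade for deaths from other causes.

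In the CRF (Protocol Annex 1), the AE table at each sunitinib follow-up visit (section 3.2) tells the site to "asses the grade using the CTCAE V4.03" and prints four boxes, 1 to 4. The AE table at each axitinib follow-up visit (section 4.2) has the same four boxes. The AE report form (Annex 2) has no grade field, but for each event it has a seriousness box "Resulted in death" and a question on relationship to study drug. The long-term follow-up form asks about AEs and death without an AE grade.

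SAP 6.2.1 lists the endpoint "Incidence of all AE per grade, especially grade 3 and 4 AE" and adds that every grade is to be considered, not only the worst. SAP 8.2.1 then lists the outputs. Its overview has rows for at least one grade 3 AE, at least one grade 4 AE and "At least one grade 3/4 AE". The tables by SOC and PT use the same three severity categories, and all of this is repeated for related AEs. Grade 5, or grade 3 and above, appears nowhere in the SAP.

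**The concern.** The protocol makes a data value mandatory that the annexed forms have no place for and that the listed severity tables would not count. A site with such an event has to improvise, and the SAP does not say how the result is to be handled.

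The possible responses push the severity figures in opposite directions. An event entered as grade 4 adds a cancer death to the grade 4 and grade 3/4 counts. An event left blank, or somehow recorded as 5, drops out of those counts, so a patient whose only severe event was the fatal one is shown as having no grade 3/4 AE. If sites differ, the grade 4 and 3/4 percentages mix the two conventions and a reader cannot tell in what proportion. Safety and tolerability of the SU-AXI sequence is a stated secondary objective, and these rows are its severity summary.

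**Working it through.** There is no arithmetic to reproduce. The check compares the grade values allowed at each step.

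| Step | Source | Grade values |
|---|---|---|
| Rule for the event leading to a malignancy death | Protocol 10.3 | 5 |
| Entry, sunitinib follow-up visit | CRF 3.2 | 1, 2, 3, 4 |
| Entry, axitinib follow-up visit | CRF 4.2 | 1, 2, 3, 4 |
| Entry, AE report form and long-term follow-up form | Annex 2; CRF 5 | no AE grade field |
| Endpoint | SAP 6.2.1 | all grades, emphasis on 3 and 4 |
| Severity rows, overview and by SOC/PT | SAP 8.2.1 | 3; 4; 3/4 |

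1. The required value 5 is not in the set {1, 2, 3, 4} that the CRF accepts. The same four boxes appear in every AE table of the CRF, so this is not a damaged table in the extracted text.
2. The value 5 is also outside every severity row of SAP 8.2.1. Adding a box to the CRF alone would not cure the problem, because the new entries would fall outside the listed rows.
3. SAP 6.2.1 is wide enough to include grade 5. The gap on the SAP side is therefore that the 8.2.1 list is narrower than the SAP's own endpoint.
4. The retrospective sunitinib AE table also has boxes 1 to 4, but it is completed only for patients enrolled at axitinib start. They survived sunitinib, so that table should not have to hold a fatal event and needs no change.
5. What the other outputs show: a fatal event stays in the All-AE and SAE tables by SOC and PT, including the related-only versions, but the SAE tables combine death with hospitalisation and the other seriousness criteria. The death summary (SAP 6.2.3 and 8.2.1) gives an all-cause proportion and a split into tumour-related and other cause, without preferred term or drug relationship. Between them, no listed output shows which AEs were fatal and which of those were considered related.
6. What the data can support: the CRF AE tables hold only description, start date and grade. The seriousness and relatedness that the SAP already tabulates must come from the AE report form, and SAP 6.2.2 explicitly draws on AE forms for discontinuations. Protocol 10.1 requires that form for all SAEs. A fatal outcome can therefore be identified per event from data the study collects.

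**The case against.** The strongest reply is that little is lost. The Grade 5 sentence concerns cancer deaths, which are not toxicity and arguably do not belong in a severe-toxicity row. Fatal events remain in the All-AE and SAE tables, deaths are summarised by period and cause, and the AE report form records fatal outcome and relatedness for each event. Protocol 8.7.3 asks for no severity summary, and SAP 4.2 rules out statistical tests, so no decision depends on these rows. SAP 6.2.1 calls for all grades, the table shells are separate documents, and the annexed CRF is V12.2 of 5 December 2014 while the protocol is V13 of 28 September 2017. A later form or shell may already have the missing category.

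Most of this stands as a limit on scope. A reader might infer that Grade 5 is required for every fatal AE, but the text limits it to a fatal outcome of the malignancy. A reader might also infer that fatal events disappear from the safety report or that their relatedness is unknown. They do not disappear, and relatedness is collected.

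The reply does not remove the mismatch. The protocol wants these cancer-death events graded, the forms it annexes cannot grade them, and no document shown says how the SAP treats them. Keeping cancer deaths out of the toxicity rows is a sound aim, but at present it would happen only where the site happened to leave the grade blank. Nothing in the documents shows a later CRF or shell that closes the gap.

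**Conclusion.** The inconsistency is real and narrow. For every event leading to a malignancy death in the period covered by Protocol 10.3, the annexed forms and the SAP 8.2.1 list offer no correct route: the event is graded 4 or lower, left ungraded, or counted in no severity row. The effect is limited to the severity summaries and to the lack of an output showing fatal AEs by preferred term and relatedness. No primary endpoint is touched.

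No event count can be given. The documents state no expected rate of such deaths, and the direction of the error depends on what sites do with the grade field. It would also go too far to call the grade 3/4 row the study's main tolerability result. The protocol's safety endpoint is the frequency of patients with at least one AE by body system.

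The conclusion assumes that the annexed CRF V12.2 reflects the eCRF in use and that the separate table shells follow the 8.2.1 list. It is worth correcting before the final analysis.

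**What to change.** - **Capture.** Either add Grade 5 to the AE tables at the sunitinib and axitinib follow-up visits, or state in the SAP that an AE with "Resulted in death" ticked on the AE report form is analysed as grade 5. The derivation is preferable: it needs no change to data already entered, and it reaches deaths first recorded on the long-term follow-up form, which has no grade field. It would also grade fatal AEs not caused by the malignancy, on which the protocol is silent, so the SAP should say that this is intended.
- **Tables.** Add Grade 5 and Grade 3 or higher rows to the overview and SOC/PT tables in SAP 8.2.1, for all AEs and for related AEs. This brings 8.2.1 into line with 6.2.1 and gives fatal AEs by preferred term and relatedness.
- **Separation.** Show deaths from disease progression apart from other fatal AEs so that they do not inflate the toxicity figures. The recorded cause of death (tumour-related or other) is available, and SAP 6.2.3 already says which form takes precedence when causes differ.

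The cost is one derivation rule, or one extra option in two eCRF tables, plus a few table rows. No new patient data are needed for the derivation.

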10.4. ADVERSE EVENT REPORTING IN THE RETROSPECTIVE SETTING

This study protocol requires human review of patient-level unstructured data; unstructured data refer to verbatim medical data, including text-based descriptions and visual depictions of medical information, such as medical records, images of physician notes, neurological scans, X-rays, or narrative fields in a database. The reviewer is obligated to report adverse events (AE) with explicit attribution to any Pfizer drug that appear in the reviewed information (defined per the patient population and study period specified in the protocol). Explicit attribution is not inferred by a temporal relationship between drug administration and an AE, but must be based on a definite statement of causality by a healthcare provider linking drug administration to the AE.

The requirements for reporting safety events on the non-interventional study (NIS) adverse event monitoring (AEM) Report Form to Pfizer Safety are as follows:

- All serious and non-serious AEs with explicit attribution to any Pfizer drug that appear in the reviewed information must be recorded on the eCRF of this study and reported, within 24 hours of awareness, to Pfizer Safety using the NIS AEM Report Form
- Scenarios involving drug exposure, including exposure during pregnancy, exposure during breast feeding, medication error, overdose, misuse, extravasation, lack of efficacy and occupational exposure associated with the use of a Pfizer product must be reported, within 24 hours of awareness, to Pfizer Safety using the NIS AEM Report Form.

For these safety events with an explicit attribution to or associated with use of, respectively, a Pfizer product, the data captured in the medical record will constitute all clinical information

known regarding these adverse events. No follow-up on related adverse events will be conducted.

All research staff members will complete the Pfizer requirements regarding training on the following: "Your Reporting Responsibilities: Monitoring the Safety, Performance and Quality of Pfizer Products (Multiple Languages)" and any relevant Your Reporting Responsibilities supplemental training. This training will be provided to all research staff members prior to study start. All trainings include a "Confirmation of Training Certificate" (for signature by the trainee) as a record of completion of the training, which must be kept in a retrievable format. Copies of all signed training certificates must be provided to Pfizer.

10.5. COUNTRY REQUIREMENT

10.5.1. Switzerland Adverse Event Reporting in the Retrospective Setting

This study protocol requires human review of patient-level unstructured data; unstructured data refer to verbatim medical data, including text-based descriptions and visual depictions of medical information, such as medical records, images of physician notes, neurological scans, X-rays, or narrative fields in a database. The reviewer is obligated to report adverse events (AE) regardless of possible attribution to a Pfizer drug.

The requirements for reporting safety events on the non-interventional study (NIS) adverse event monitoring (AEM) Report Form to Pfizer Safety are as follows:

- All serious and non-serious AEs that appear in the reviewed information must be recorded on the eCRF of this study and reported, within 24 hours of awareness, to Pfizer Safety using the NIS AEM Report Form
- Scenarios involving drug exposure, including exposure during pregnancy, exposure during breast feeding, medication error, overdose, misuse, extravasation, lack of efficacy and occupational exposure associated with the use of a Pfizer product must be reported, within 24 hours of awareness, to Pfizer Safety using the NIS AEM Report Form.

For these safety events, the data captured in the medical record will constitute all clinical information known regarding these adverse events. No follow-up on related adverse events will be conducted.

10.5.2. Notification of adverse events / adverse reactions in the retrospective area of Spain

This notification has not been expressly requested by the AEMPS at the time of registration of the study.

